1.2. Risk Benefit Section

1.2.1. Known Benefits

The clinical benefit of prime-boost combinations of Ad26.ZEBOV and MVA-BN-Filo is to be established.

1.2.2. Potential Benefits

Subjects may benefit from clinical testing and physical examination; others may benefit from knowledge gained in this study that may aid in the development of an Ebola vaccine.

1.2.3. Known Risks

See the safety data presented in Section 1.1, Background.

1.2.4. Potential Risks

The following potential risks for Ad26.ZEBOV and MVA-BN-Filo will be monitored during the study and are specified in the protocol:

Risks Related to Vaccines

Subjects may exhibit general signs and symptoms associated with administration of a vaccine, or a placebo vaccination, including fatigue, nausea, headache, vomiting, myalgia, rash, arthralgia, general itching, fever, and chills. In addition, subjects may experience local (injection site) reactions such as pain/tenderness, erythema, induration, swelling, itching and/or warmth at the injection site. These events will be monitored, but are generally short-term and do not require treatment.

Subjects may have an allergic reaction to the vaccination. An allergic reaction may cause a rash, hives or even difficulty breathing. Severe reactions are rare. Medications must be available in the clinic to treat serious allergic reactions.

The risks related to vaccine induced seropositivity (VISP) are discussed in Section 9.4, Vaccine Induced Seropositivity.

Risk of Myo/Pericarditis

While replicating smallpox vaccines have been associated with an increased risk to develop myo/pericarditis,²⁰ this has not been observed with MVA-BN and is not expected with this highly

attenuated, non-replicating vaccine. Based on observations with first- and second-generation replication-competent smallpox vaccines, particular attention has been placed on the monitoring for cardiac signs and symptoms in all clinical studies using MVA-BN. Despite the close cardiac monitoring, no event indicating a case of myo/pericarditis has been observed in any completed MVA-BN study. In a review of prospective surveillances for cardiac adverse events in 6 different clinical studies in 382 subjects receiving MVA vaccines, only 1 subject (0.3%) met the criteria for vaccine-induced myocarditis and eventually the subject was found to suffer from exercise-induced palpitations. Self-limited mild elevations in troponin I were recorded in 3 (0.8%) subjects without evidence of myo/pericarditis.⁷

For the present study, subjects will be actively screened to exclude pre-existing cardiac concerns and enrolled subjects will be monitored during the study.

Pregnancy and Birth Control

The effect of the study vaccines on a fetus or nursing baby is unknown, as well as the effect on semen, so women of childbearing potential, and men having sexual intercourse with women, are required to agree to practice adequate birth control measures for sexual intercourse from 28 days before the prime vaccination until at least 3 months after the boost vaccination (see Section 9.1.3, Screening). Women who are pregnant or breast-feeding, or are planning to become pregnant while enrolled in the study or within 3 months after the boost vaccination, will be excluded from enrollment into the study.

Women of childbearing potential must also agree not to donate eggs (ova, oocytes) for the purposes of assisted reproduction from the start of screening onwards until at least 3 months after the boost vaccination. Men must also agree not to donate sperm from the start of screening onwards until at least 3 months after the boost vaccination.

Note: after the main study is unblinded, placebo subjects may stop birth control measures or resume their pre-study birth control measures, and may donate eggs (females) or sperm (males).

Risks from Blood Draws

Blood draws may cause pain, bruising, bleeding, and, rarely, infection at the site where the blood is taken.

Unknown Risks

There may be other serious risks that are not known.

1.2.5. Overall Benefit/Risk Assessment

Based on the available data and proposed safety measures, the overall risk/benefit assessment for this clinical study is acceptable for the following reasons:

- There is no previous clinical experience with MVA-BN-Filo or Ad26.ZEBOV. However, safety data generated with the 2 vaccines with different inserts have revealed no significant safety issues (see Section 1.1).

- Only subjects who meet all inclusion criteria and none of the exclusion criteria (specified in Sections 4.1 and 4.2, respectively) will be allowed to participate in this study. The selection criteria include adequate provisions to minimize the risk and protect the well-being of subjects in the study.
- Safety will be closely monitored throughout the study:
 - After each vaccination, subjects will be observed directly for 30 minutes and remain at the site for a total of 60 minutes post-vaccination to monitor the development of any acute reactions, or longer in case of grade 3 adverse events. Subjects will use a diary to document symptoms of unsolicited and solicited local and systemic adverse events in the evening after each vaccination and then daily for the next 7 days.
 - The investigator or the designee will document unsolicited adverse events from signing of the informed consent form (ICF) onwards until 21 days post-boost, and serious adverse events and adverse events related to blood draws from signing of the ICF onwards until the end of the study.
 - Safety measures, including laboratory tests, vital sign measurements, electrocardiograms (ECGs), and physical examinations, will be performed at scheduled visits during the study.
 - Any clinically significant abnormalities persisting at the end of the study or upon early withdrawal will be followed by the investigator until resolution or until a clinically stable endpoint is reached.
- Several safety measures are included in this protocol to minimize the potential risk to subjects, including the following:
 - The safety evaluations described in Section 0 take into account adverse events of interest based on clinical safety data and available nonclinical data.
 - There are predefined pausing rules (see Section 11.8) that would result in pausing of further vaccination if predefined conditions occur, preventing exposure of new subjects to study vaccine until an internal Data Review Committee (DRC) reviews all safety data. Study enrollment would be resumed only if the DRC recommends it.
 - Subjects will be withdrawn from study vaccine administration for the following reasons (see also Section 10.2, Discontinuation of Study Vaccine):
 - Any reason listed in Section 11.8, Pausing Rules, preventing a subject from receiving boost vaccination
 - Pregnancy
 - Any adverse event considered at least possibly related to the study vaccine, worsening of health status or intercurrent illnesses that, in the opinion of the investigator, requires discontinuation from study vaccine
 - Confirmed Ebola disease
 - Use of disallowed medications listed in Section 8, Prestudy and Concomitant Therapy.

- If acute illness (excluding minor illnesses such as diarrhea or mild upper respiratory tract infection) or fever (oral temperature ≥ 38.0 °C) occur at the scheduled time for vaccination, the subject may be vaccinated up to 10 days beyond the window allowed for the scheduled vaccination, or be withdrawn from that vaccination at the discretion of the investigator and after consultation with the sponsor (see Section 10.3).
- If a subject withdraws from the study (withdrawal of consent), he/she maintains the option to participate in the safety follow-up.

1.3. Overall Rationale for the Study

In nonclinical studies in the *Cynomolgus* macaque model, heterologous prime-boost regimens of a multivalent mixture of Ad26 vectors (each expressing EBOV Mayinga, SUDV or MARV GP) and MVA-BN-Filo provided complete protection against the highly pathogenic wild-type EBOV Kikwit 1995 variant (report pending). Further nonclinical studies are ongoing to evaluate the protection of the multivalent vaccine regimen in additional animals and to assess the protective efficacy of a combination regimen of Ad26.ZEBOV and MVA-BN-Filo (either a simultaneous administration or as prime-boost regimen).

In humans, both Ad26- and MVA-based vaccines containing various antigenic inserts have been shown to be safe and immunogenic (see Section 1.1, Background). To date, more than 200 subjects have received Crucell Ad26-based vaccines in clinical studies. The MVA-BN platform is the basis of the non-replicating smallpox vaccine registered in Canada and Europe, and has been safely used in more than 7,500 humans.¹⁴ Although routinely used by the subcutaneous route, MVA-BN at a dose of 1×10^8 TCID₅₀ (50% Tissue Culture Infective Dose) has been demonstrated to be as safe and immunogenic when used by the IM route.^{8,24} The IM route has been chosen for the present study for blinding purposes.

The unprecedented size and scale of the ongoing Ebola disease outbreak that started in December 2013 in Guinea and subsequently spread to Sierra Leone, Nigeria and Liberia, led to the outbreak being declared a public health emergency of international concern in August 2014 by the WHO. This study is one of a series of studies to evaluate the heterologous combination of Ad26.ZEBOV and MVA-BN-Filo as a possible vaccine regimen to prevent Ebola disease. It will test schedules that will be evaluated in planned NHP challenge studies.

2. OBJECTIVES AND HYPOTHESIS

2.1. Objectives

This first-in-human study aims to evaluate the safety, tolerability and immunogenicity of different MVA-BN-Filo and Ad26.ZEBOV vaccine regimens.

Primary Objectives

- To assess the safety and tolerability of heterologous prime-boost regimens utilizing MVA-BN-Filo at a dose of 1×10^8 TCID₅₀ and Ad26.ZEBOV at a dose of 5×10^{10} vp.

Secondary Objectives

- To assess humoral and cellular immune responses to the EBOV GP of the various regimens tested as measured by virus neutralization assay, ELISA and ELISpot assay.

Exploratory Objectives

- To explore further humoral and cellular immune responses to the EBOV GP and the adenovirus and MVA backbone of the various regimens tested. The assays to be used may include, but will not be limited to, adenovirus/MVA neutralization assays, molecular antibody characterization, and intracellular cytokine staining (ICS).
- To explore humoral and cellular immune responses to the SUDV GP, MARV GP and TAFV NP if assays are available.

2.2. Hypothesis

No formal statistical hypothesis testing is planned.

3. STUDY DESIGN AND RATIONALE

3.1. Overview of Study Design

This Phase 1 first-in-human study consists of 2 parts.

The main study is a randomized, placebo-controlled, observer-blind study evaluating the safety, tolerability and immunogenicity of 4 regimens using MVA-BN-Filo at a dose of 1×10^8 TCID₅₀ and Ad26.ZEBOV at a dose of 5×10^{10} vp: 2 regimens will have MVA-BN-Filo as prime and Ad26.ZEBOV as boost at a 28- or 56-day interval, and 2 regimens will have Ad26.ZEBOV as prime and MVA-BN-Filo as boost at a 28- or 56-day interval. The main study will be conducted in approximately 72 healthy adult subjects who never received an experimental Ebola candidate vaccine before and have no known exposure to or diagnosis of Ebola disease.

The substudy consists of an open-label, uncontrolled non-randomized treatment arm evaluating the safety, tolerability and immunogenicity of a regimen with Ad26.ZEBOV at a dose of 5×10^{10} vp as prime, and MVA-BN-Filo at a dose of 1×10^8 TCID₅₀ as boost 14 days later, and will be conducted in approximately 15 healthy adult subjects.

The study consists of a screening period (of up to 28 days in the main study and up to 56 days in the substudy), a vaccination period in which subjects will be vaccinated at baseline (Day 1) followed by a boost on Day 15, 29 or 57, and a post-boost follow-up until all subjects have had their 21-day post-boost visit (Day 36, 50 or 78) or discontinued earlier. The main study will be unblinded when all subjects in the main study have had their 21-day post-boost visit or discontinued earlier. After unblinding, subjects who received placebo will be contacted to communicate that they have completed the study and do not need to contact the site any longer. The subjects who received active vaccine will enter a long-term follow-up, with visits on Day 180 (± 15 days), Day 240 (± 30 days) and Day 360 (± 30 days) post-prime.

The Principal Investigator (who is blinded to treatment in the main study) will be responsible for the safety monitoring of the study. If at least one pre-specified pausing rule is met, vaccinations will be paused and an internal DRC meeting will be convened. For details on the DRC, see Section 11.7. For details on the pausing rules, see Section 11.8.

Subjects in the main study will be enrolled into 4 different groups of 18 healthy subjects each. Overall, subjects will be randomized within group in a 5:1 ratio to receive active vaccine or placebo (0.9% saline) through IM injections (0.5 mL) as follows:

- MVA-BN-Filo (1×10^8 TCID₅₀) on Day 1, followed by a booster of Ad26.ZEBOV (5×10^{10} vp) on Day 29 (Group 1) or Day 57 (Group 2), or
- Ad26.ZEBOV (5×10^{10} vp) on Day 1, followed by a booster of MVA-BN-Filo (1×10^8 TCID₅₀) on Day 29 (Group 3) or Day 57 (Group 4).

Enrollment of subjects in Groups 1 and 3 will start with vaccination of 1/1 subjects (active vaccine/placebo; Sentinel Cohort) to assess the tolerability of the 2 study vaccines over a 24-hour period before exposing larger cohorts of subjects to the vaccines. Subjects will be contacted by telephone after at least 24 hours to verify the absence of any predefined events (ie, a serious adverse event considered to be related to any of the study vaccines, signs of anaphylaxis or generalized urticaria clearly attributable to study vaccination, a severe [grade 3] unsolicited adverse event considered to be related to any of the study vaccines, a severe [grade 3] solicited injection site reaction, a severe [grade 3] solicited systemic adverse event considered to be related to any of the study vaccines, or death). Enrollment of the next cohorts will be as follows:

- Groups 1 and 3: 4/1 subjects (active vaccine/placebo; Cohort 1) followed, in the absence of any of the above-mentioned events, confirmed by a telephone call with each subject after at least 24 hours after the prime vaccination, by 10/1 subjects (active vaccine/placebo; Cohort 2)
- Groups 2 and 4: 5/1 subjects (active vaccine/placebo; Cohort 1) followed, in the absence of any of the above-mentioned events, confirmed by a telephone call with each subject after at least 24 hours after the prime vaccination, by 10/2 subjects (active vaccine/placebo; Cohort 2)

The enrollment of all subjects of Cohort 1 will be carried out ideally on the same day. Also the enrollment of all subjects of Cohort 2 will be carried out ideally on the same day. If enrollment of Cohort 1 is carried out over more than 1 day, enrollment of Cohort 2 in that group will only start after at least 24 hours after the prime vaccination in the last subject in Cohort 1.

Enrollment in the open-label substudy (Cohort 3) will start after the prime vaccination in the last subject in Cohort 2. Subjects will receive active vaccine through IM injections (0.5 mL) as follows:

- Ad26.ZEBOV (5×10^{10} vp) on Day 1, followed by a booster of MVA-BN-Filo (1×10^8 TCID₅₀) on Day 15 (Group 5).

Groups 2 and 4 will test a schedule that has already provided protection in an NHP challenge study (though with a higher dose of MVA-BN-Filo [ie, 5×10^8 TCID₅₀] and with Ad26-Tri, which is a trivalent candidate vaccine expressing the EBOV Mayinga, SUDV and MARV GPs) and will therefore serve as reference schedule. Groups 1 and 3 will test a shorter schedule that will be tested in planned NHP challenge studies. Group 5 will explore a schedule that may be further evaluated in future studies.

The study enrollment plan is summarized in Table 6. The different study vaccination schedules are summarized in Table 7.

Table 6: Study Enrollment Plan

Group	Sentinel Cohort	Cohort 1 ^{a)}	Cohort 2 ^{b)}	Cohort 3 ^{c)}
1	1:1 (active vaccine/placebo)	4:1 (active vaccine/placebo)	10:1 (active vaccine/placebo)	
2	-	5:1 (active vaccine/placebo)	10:2 (active vaccine/placebo)	
3	1:1 (active vaccine/placebo)	4:1 (active vaccine/placebo)	10:1 (active vaccine/placebo)	
4	-	5:1 (active vaccine/placebo)	10:2 (active vaccine/placebo)	
5	-	-	-	15 (active vaccine)

a) Cohort 1 will be enrolled after at least 24 hours after the prime vaccination in the Sentinel Cohorts.

b) Cohort 2 will be enrolled after at least 24 hours after the prime vaccination in the last subject in Cohort 1.

c) Cohort 3 will be enrolled after the prime vaccination in the last subject in Cohort 2 for operational/logistic reasons.

Table 7: Study Vaccination Schedules

Group	N	Day 1	Day 15	Day 29	Day 57	
1	18	15	MVA-BN-Filo 1×10^8 TCID ₅₀	-	Ad26.ZEBOV 5×10^{10} vp	-
		3	placebo (0.9% saline)	-	placebo (0.9% saline)	-
2	18	15	MVA-BN-Filo 1×10^8 TCID ₅₀	-	-	Ad26.ZEBOV 5×10^{10} vp
		3	placebo (0.9% saline)	-	-	placebo (0.9% saline)
3	18	15	Ad26.ZEBOV 5×10^{10} vp	-	MVA-BN-Filo 1×10^8 TCID ₅₀	-
		3	placebo (0.9% saline)	-	placebo (0.9% saline)	-
4	18	15	Ad26.ZEBOV 5×10^{10} vp	-	-	MVA-BN-Filo 1×10^8 TCID ₅₀
		3	placebo (0.9% saline)	-	-	placebo (0.9% saline)
5	15	Ad26.ZEBOV 5×10^{10} vp	MVA-BN-Filo 1×10^8 TCID ₅₀	-	-	

N: number of subjects to receive study vaccine; TCID₅₀: 50% Tissue Culture Infective Dose; vp: viral particles

After each vaccination, subjects will be observed directly for 30 minutes and remain at the site for a total of 60 minutes post-vaccination to monitor for the development of any acute reactions, or longer in case of grade 3 adverse events. Subjects will be instructed to contact the investigator

immediately if they experience any adverse event that they perceive as relevant or possibly related to study vaccine in their opinion, and will be contacted after at least 24 hours for collection of adverse events and to confirm that no pre-specified pausing rules have been met. Subjects will use a diary to document symptoms of unsolicited and solicited local and systemic adverse events in the evening after each vaccination and then daily for the next 7 days. The investigator or the designee will document unsolicited adverse events from signing of the ICF onwards until 21 days post-boost, and serious adverse events and adverse events related to blood draws from signing of the ICF onwards until the end of the study. In addition, the investigator or designee will collect samples for safety assessments (hematology, chemistry, and urinalysis) and assessments of immune responses, at the time points indicated in the [Time and Events Schedule](#).

The final analysis will be performed when all subjects have completed the last study-related visit or discontinued earlier.

Subjects will be approached to consent for enrollment into the VAC52150 Vaccine Development Registry Protocol for long-term surveillance after completing the present study (see Section 9.1.7 for details).

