reactogenicity comprised moderate injection site pain/tenderness and/or moderate to severe erythema which resolved within 3 days of vaccination. Transient systemic reactogenicity comprised headache, chills, joint pain, myalgia, malaise/fatigue, and fever. No deaths or vaccine-related serious adverse events were observed. Vaccination elicited both systemic and mucosal Env-specific humoral and cellular immune responses. No increased activated total or vector-specific mucosal CD4 T-lymphocytes following vaccination were detected in the colorectal mucosa, indicating that vaccination with Ad26 did not increase mucosal inflammation.^{1,2}

- In study IPCAVD-004 (n=217), the safety and immunogenicity of IM doses of Ad26.ENVA.01 and Ad35.ENV (an Ad35 vector expressing an HIV envelope GP used in that study at a dose of 5×10^{10} vp), given in heterologous and homologous prime-boost regimens at 3- versus 6-month intervals, was evaluated. There were 452 adverse events reported by 84 of 176 Ad26-vaccine recipients (47.7%), the majority being mild (75.5%) in severity. The proportion of subjects with moderate or severe symptoms was not statistically significantly different between vaccine and placebo. There were 3 serious adverse events: 2 serious adverse events in placebo recipients (grade 3 peritonsillar abscess and grade 4 migraine headache, both resolved with no residual effects) and 1 serious adverse event in an Ad35/Ad26 vaccine recipient (grade 4 acute myelogenous leukemia, resolved with sequelae). No deaths or vaccine-related serious adverse events were reported. Overall, 97% to 100% of subjects developed anti-Env binding antibodies (enzyme-linked immunosorbent assay [ELISA]) after a second dose, with heterologous and homologous regimens being comparable. Immune responses in groups who received 3-month and 6-month schedules were comparable. Four weeks post-vaccination, interferon (IFN)- γ enzyme-linked immunospot (ELISpot) showed response rates between 44% and 100%. The heterologous and homologous regimens were comparable. There was induction of Ad26-neutralizing antibodies in the majority of vaccine recipients after 2 immunizations with Ad26.ENVA.01.¹⁹

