11.8. Pausing Rules

The Principal Investigator and the designated co-investigators will review the safety of enrolled subjects on an ongoing basis.

If any pausing rule is met, and following an internal safety review it is deemed appropriate to restart dosing, a request to restart dosing with pertinent data must be submitted to health authorities as a request for a substantial amendment. Communications from the DRC will be forwarded by the investigator to the IRB/IEC and by the sponsor to relevant health authorities.

The following pausing rules apply to the Sentinel Cohorts. These pausing rules will prevent the start of enrollment of Cohort 1 and will trigger a DRC meeting:

1. One subject experiences anaphylaxis or generalized urticaria clearly attributable to study vaccination within 24 hours of the prime vaccination; *OR*
2. One subject experiences a serious adverse event that is considered to be related to any of the study vaccines; *OR*
3. One subject experiences a severe (grade 3) unsolicited adverse event that is considered to be related to any of the study vaccines; *OR*
4. One subject experiences a severe (grade 3) solicited injection site reaction. (The size [measured in mm] of erythema will not be used as a pausing criterion); *OR*
5. One subject experiences a severe (grade 3) solicited systemic adverse event considered to be related to any of the study vaccines. (Subjective systemic adverse event corroborated by study personnel.); *OR*
6. Death of a subject.

The following pausing rules apply to Cohort 1 of any group in the main study. These pausing rules will prevent the start of enrollment of Cohort 2 and will trigger a DRC meeting:

1. One subject experiences anaphylaxis or generalized urticaria clearly attributable to study vaccination within 24 hours of prime vaccination; *OR*
2. One subject experiences a serious adverse event that is considered to be related to any of the study vaccines; *OR*
3. One subject experiences a severe (grade 3) unsolicited adverse event that is considered to be related to any of the study vaccines; *OR*
4. One subject experiences a severe (grade 3) solicited injection site reaction. (The size [measured in mm] of erythema will not be used as a pausing criterion); *OR*
5. One subject experiences a severe (grade 3) solicited systemic adverse event considered to be related to any of the study vaccines. (Subjective systemic adverse event corroborated by study personnel.); *OR*
6. Death of a subject.

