3. A serious adverse event that is considered to be related to any of the study vaccines; *OR*
4. A severe (grade 3) (non-serious) laboratory abnormality (including unexplained hematuria) that is considered to be related to any of the study vaccines; *OR*
5. A severe (grade 3) (non-serious) unsolicited adverse event that is considered to be related to any of the study vaccines; *OR*
6. A severe (grade 3) (non-serious) solicited injection site reaction that does not recover within 48 hours, *OR*
7. A severe (grade 3) (non-serious) solicited systemic adverse event considered to be related to any of the study vaccines that does not recover within 48 hours.

Vaccinations for an individual subject may be suspended for safety concerns other than those described above, at the discretion of the investigator if he/she feels the subject's safety may be threatened. The investigator may ask for a review meeting to be held for any single event or combination of multiple events which, in his/her professional opinion, jeopardize the safety of the subjects or the reliability of the data.

Vaccinations for the study may be suspended for safety concerns other than those described above or before pausing rules are met if in the judgment of investigator, subject safety may be threatened. The sponsor should be notified that the DRC will need to be convened.

If a pause is installed, vaccinations will be held until DRC review is complete. Resumption of vaccination may be determined by the DRC following cumulative review of the available safety data as outlined in the charter. The site will be allowed to resume activities upon receipt of a written notification from the sponsor. As applicable, the appropriate regulatory authorities will be informed in writing of the decision by the DRC to resume or discontinue study activities. The site is responsible for notifying their IRB/IEC according to local standards and regulations. The sponsor is responsible for notifying the regulatory authorities.

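### Sections 3.1 and 11.8 list different events for opening the next cohort: isolated grade 3 erythema blocks it under one and not the other

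*Protocol*

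**What the plan says.** Section 3.1 (Overview of Study Design) requires a telephone contact at least 24 hours after the prime vaccination "to verify the absence of any predefined events (ie, a serious adverse event considered to be related to any of the study vaccines", and the bracket then continues to the end of the list. The list includes "a severe [grade 3] solicited injection site reaction, a severe [grade 3] solicited systemic adverse event considered to be related" to study vaccine. It sets no condition on the type of local reaction. Cohort 2 is then "followed, in the absence of any of the above-mentioned events, confirmed by a telephone call with each subject". The Synopsis repeats the list in the same form.

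Section 11.8 (Pausing Rules) sets out rules for the Sentinel Cohorts, which prevent the start of Cohort 1, and for Cohort 1, of which it says: "These pausing rules will prevent the start of enrollment of Cohort 2 and will trigger a DRC meeting". The local-reaction rule carries the note "The size [measured in mm] of erythema will not be used as a pausing criterion", and the systemic rule carries the note "Subjective systemic adverse event corroborated by study personnel". The anaphylaxis and generalized urticaria rule is limited to the 24 hours after the prime vaccination. Section 3.1 has none of these three qualifiers.

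Section 3.1 also refers the reader to Section 11.8 for the details of the pausing rules. Later in Section 3.1, and again in Section 9.1.4, the 24-hour contact is said to confirm that no pausing rule has been met.

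**The concern.** Both sections are operative for the same decision. Section 3.1 makes enrolment of the next cohort depend on its own list, and Section 11.8 prevents that enrolment when one of its rules is met. Where the lists differ, a site that follows the protocol can reach opposite answers on whether more first-in-human subjects may be vaccinated.

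The case is foreseeable. Section 1.1 (Background) reports, for an Ad26 vector with a different insert at the same 5x10^10 vp dose, "moderate to severe erythema which resolved within 3 days of vaccination".

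The consequences differ as well. Meeting a Section 11.8 rule triggers a DRC meeting, and a restart needs a substantial-amendment request to the health authorities. A block that arises only from the Section 3.1 list has no defined DRC trigger.

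**Working it through.** **Step 1. The two lists side by side.**

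| Item | Synopsis and Section 3.1 | Section 11.8, Sentinel and Cohort 1 rules |
|---|---|---|
| Grade 3 solicited injection site reaction | Counts, no exception | Counts, erythema size excluded |
| Related grade 3 solicited systemic event | Counts, silent on corroboration | Counts, with corroboration of subjective events |
| Attributable anaphylaxis or generalized urticaria | Counts, no time limit | Counts within 24 hours of prime |
| Related serious event, related grade 3 unsolicited event, death | Counts | Counts |
| Stated effect | Next cohort not opened | Next cohort not opened, DRC meeting |

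**Step 2. What the erythema exclusion removes.** Section 9.3.2 lists erythema among the solicited local reactions, so Section 3.1 covers it. Attachment 1 grades erythema as 2.5-5 cm (grade 1), 5.1-10 cm (grade 2) and >10 cm (grade 3). Its footnote adds a functional scale for induration/swelling only. The general scale in Section 12.1.3 applies only to events not in the table. Grade 3 erythema is therefore the same thing as erythema above 10 cm. Once size is excluded, no grade 3 erythema can meet the Section 11.8 rule, while every grade 3 erythema meets the Section 3.1 list.

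**Step 3. The other two differences.** On corroboration, Section 3.1 is silent and not contrary. On anaphylaxis and generalized urticaria, Attachment 1 grades both as grade 3 allergic reactions. A related case after 24 hours would usually be caught by the Section 11.8 rules on related grade 3 events anyway. These are differences of wording with small effect; the erythema difference changes the answer.

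**Step 4. Method check.** The protocol's own Table 11 uses P(at least one) = 1-(1-p)^n with n = 15. At p = 1%, 2.5%, 5%, 10% and 20% this gives 13.99%, 31.6%, 53.7%, 79.4% and 96.48%. The table states 14%, 32%, 54%, 79% and 96%, so it is reproduced and not in dispute.

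**Step 5. Illustration per gate.** The active, Ad26-primed subjects at each gate come from Table 6: 1 (Group 3 Sentinel), 4 (Group 3 Cohort 1) and 5 (Group 4 Cohort 1). The rate p is assumed, because the documents give none.

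| Assumed p | n = 1 | n = 4 | n = 5 |
|---|---|---|---|
| 1% | 1% | 3.9% | 4.9% |
| 2.5% | 2.5% | 9.6% | 11.9% |
| 5% | 5% | 18.5% | 22.6% |
| 10% | 10% | 34.4% | 41.0% |
| 20% | 20% | 59.0% | 67.2% |

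For example, 1-0.95^4 = 1-0.8145 = 18.5% and 1-0.95^5 = 1-0.7738 = 22.6%. This is the chance that erythema alone would meet the Section 3.1 list. Under Section 11.8 it is 0 at every p. The chance that the two sections disagree is somewhat lower than the table shows. It also requires that the erythema be known by the time of the check and that no other listed event be present, since grade 3 pain or swelling, for example, meets both lists.

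**The case against.** The best defence is that Section 11.8 is the detailed text and Section 3.1 an overview. Section 3.1 points to Section 11.8, the 24-hour contact is said to confirm the pausing rules, and the erythema exclusion appears in every set of study-level rules. This lowers the severity but does not settle the matter. Section 3.1 writes its list as a closed definition and makes enrolment depend on it. It does not say that the list is abbreviated or that Section 11.8 prevails.

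It can also be said that the stricter literal reading only delays enrolment. That is fair, but the other reading lets the next cohort start after an event that Section 3.1 says must be absent.

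Several stronger readings are tempting and are not supported:

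- *A block under Section 3.1 alone could never be lifted, or erythema could never pause the study.* Section 11.8 requires analysis of all grade 3 cases whether or not a pausing rule is met. It also lets the investigator ask for a review of any single event or suspend vaccination for other safety concerns. What is missing is a defined DRC trigger.
- *Section 3.1 counts uncorroborated systemic events, and corroboration cannot be had in time.* Section 3.1 is only silent. The call has no upper time limit, and Section 9.1.1 allows extra visits.
- *The boost rule contradicts the exclusion.* Section 11.8 withholds the boost after "A severe (grade 3) (non-serious) solicited injection site reaction that does not recover within 48 hours", with no erythema exception. That is a decision about one subject and may have its own threshold.
- *The probabilities should be pooled over all 10 Ad26-primed subjects in the Sentinel Cohort and Cohort 1.* Section 3.1 sets out the sequence group by group, so the gates are separate and pooling overstates the chance at any one decision.
- *The earlier Ad26 data show grade 3 erythema as defined here.* Section 1.1 gives no rate and no grading scale, and the insert was different.

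**Conclusion.** The contradiction stands, and it should be fixed. Isolated grade 3 erythema in a Sentinel or Cohort 1 subject blocks the next cohort under the Synopsis and Section 3.1 and does not under Section 11.8. This conclusion rests on the wording and on the grading in Attachment 1, and needs no assumed rate. How often it would arise cannot be derived from the documents; the 5%, 18.5% and 22.6% per gate hold only at the assumed 5%. Each Cohort 2 gate governs exposure of 10 further active subjects in that group. The differences on corroboration and on the 24-hour limit are real but minor. Sample size, endpoints and analyses are untouched.

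**What to change.** Reconcile the Synopsis, Section 3.1 and Section 11.8 so that one event list, with the same qualifiers, governs each cohort step, or state which section prevails. The reconciliation should cover the erythema exclusion, the corroboration of subjective systemic events and the 24-hour limit on anaphylaxis and generalized urticaria. It should also say whether any event that holds back a cohort triggers a DRC meeting. Which events count is for the sponsor and the DRC to decide. The cost is wording in three places at the next amendment, with no added subjects, visits or tests.
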